### 18.3.5 Interim analysis

No interim analysis will be conducted as all medical devices utilized are CE marked and suitable for performing the test procedures. Additionally, the sample size is relatively small and the time horizon correspondingly short.

## 18.4 Deviations from the Statistical Plan

It is unlikely that the statistical plan will change during the short trial period since the interim analysis is excluded. Any deviations in the statistical plan will be reported in the final study report.

## 18.5 Pass/fail criteria

All patients included in the results must fulfill the inclusion and exclusion criterion.

### Primary outcome:

- Number of times the tube position needs to be verified with a scope.  
 Must be stated in integers.

### Secondary outcomes:

- Intubation time (seconds)
  - There must be a time difference between the DLT entering the patient and the correct DLT positioning is verified. Must be stated in seconds.
- Number of intubation attempts
  - Must be stated in integers.
- Number of times incorrect placement of the tube is prevented during intubation
  - Must be stated in integers.
- Number of times the tube needs to be repositioned during intubation
  - Must be stated in integers
- Number of times where the physician prevents repositioning of the tube during surgery
  - Must be stated in integers.
- Number of times the tube needs to be repositioned during surgery
  - Must be stated in integers and the reposition time must be positive in cases where repositioning has been reported
- Reposition time (seconds) during surgery
  - The time must be positive in cases where that the tube has been repositioned.
- Number of times the surgeon stops working while the tube is repositioned

# Clinical Investigation Plan (CIP)

Study Name: VivaSight-DL study (CIS-009)  
 Ethical committee number: S-20180081

CLI-000427

Rev. 02

- Must be stated in integers, reposition time must be positive and in must be reported that a tube needs to be repositioned
- Number of times the backup anesthesiologist is called into the operating room for assistance
  - Must be stated in integers
- Time the back-up anesthesiologist spends on the procedure
  - No predetermined pass/fail criterion

## Tertiary end-point

- Qualitative measures (questions to the patient)
- Qualitative measures (questions to the person who intubated)
- No predetermined pass/fail criterion

## 18.6 Data file

Copies of CRFs, Patient Registration List, and informed consents will be kept on the investigation site in accordance with local regulations or at least for a period of 5 years after the investigator has signed the final Investigation report. Moreover, the investigator site file is filed accordingly. Ambu will file the original CRFs for the rest of the products' lifetime + 5 years. Moreover, Adverse Event Forms, Statistical Analysis, agreements, approvals, Investigators' CVs, CIP, and CIR will also be filed.

## 18.7 Health economic evaluation

The cost of all relevant processes related to single-lung ventilation will be summed and the average cost per procedure will create the cost input into a cost-effectiveness model. Capital costs will be discounted at the national appropriate discount rate of 4.05 and depreciated over the assumed life span of the device (14).

The effects measures included in the cost-effectiveness model includes:

- The primary outcome: the risk of needing a bronchoscope to check DLT placement
- The subsequent risk of cross-infection due to bronchoscopy. This risk is calculated based on current evidence from the literature

Cost-effectiveness data will be analyzed as a base-case result via a decision tree running over a short time period of one year within the hospital setting where the procedure is taking place. This will result in the deterministic ICER.

The cost data, risks and base-case will be presented in a table.

To challenge the base-case robustness several 1-way deterministic sensitivity analyses will be conducted. Doing so, major contributors to the base-case result will be varied to test their contribution to the base-case. The one-way sensitivity results will be presented as a tornado plot. To validate the overall robustness and second order uncertainty of the base-case a probabilistic sensitivity analysis will be conducted. Here, all the stochastic variables contributing to the ICER will be varied simultaneously. The probabilistic sensitivity analysis will be presented in a cost-effectiveness plane.

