## 4. END POINTS

### Primary end-point:

- Number of times where fiberoptic confirmation of tube position during intubation or surgery is needed

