## 7.10 Collection of cost data

To enable an exact cost-model of single-lung ventilation, it is necessary to fully understand all processes related to the procedure. A research assistant will map all processes related to the procedure at the investigational site. Based on this, the research assistance collects all costs related to single-lung ventilation.

Resources and personnel time used for the individual processes will be tracked on a worksheet based on the initial mapping of the processes related to single-lung ventilation. This includes but is not excluded to personnel cost, procedure times, utilities, single-use equipment and capital equipment used during single-lung ventilation. Furthermore, all resources and times related to bronchoscopes will be collected via following at least 5 bronchoscopes from storage/drying cabinets through procedure, cleaning, reprocessing and back to storage/drying cabinets.

The following cost data will be collected via the investigational sites own records: Capital cost, repair costs, maintenance cost, cost of service agreements, cleaning verification costs, audit costs, personnel costs, cost of single-use equipment, administrative costs, cost of utilities and detergents. Note that if additional related costs are detected during the study they will be included in the cost-model.

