## Case Report Form – Comparison of VivaSight-DL and Conventional DLT

### Product Information

Subject is randomized to:	 Test group (VivaSight-DL)	 Control group (Shiley)
---------------------------	--	---

Product information should only be filled out for the products being used.

Tube information	 aView monitor information (only applies for the test group)
Lot. No:	Lot. No:
Size (Fr)	 35  37  39  41

Supplementary products	Brand	Model	Additional information
Direct laryngoscope			
FOB			

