### Data collection

Type of surgery	Date of surgery	Knife start (hh:mm)	Knife end (hh:mm)
 Open  Keyhole			

**Intubation** (the period from the direct laryngoscope is introduced into the subject's mouth until correct bronchial cuff placement is verified by capnography)

Bronchoscope use (n)	Repositioning prevented (n)	Tube repositioned (n)	Intubation attempts (n)	Intubation time (sec)
				sec.

Cormack-L classification	Smooth intubation?	Need to bend tube?	Resistance during tube placement?	Need of suction after tube placement?
 1  2  3  4	 Yes  No			

Bronchial cuff pressure	Tracheal cuff pressure	Comments:
Cm H 2 O	Cm H 2 O	

**Surgery** (the period from correct bronchial cuff placement is verified by capnography until the DLT exits the subject's mouth)

Bronchoscope use (n)	Repositioning prevented (n)	Tube repositioned (n)

Repositioning of tube	Time used to reposition the tube	Rate of restriction on the surgical procedure	Responsible anesthesiologist assisted	Time spend by responsible anesthesiologist
1 st repositioning	sec	 Not restricted  Restricted  Completely restricted	 Yes  No	sec
2 nd repositioning	sec	 Not restricted  Restricted  Completely restricted	 Yes  No	sec
3 rd repositioning	sec	 Not restricted  Restricted  Completely restricted	 Yes  No	sec

Extubation of the subject	Smooth extubation?	Did the subject cough?	Did the subject complain of throat pain?
	 Yes  No	 Yes  No	 Yes  No

Comments:

Any adverse events/adverse device effects?		
Yes	No	If yes: please specify (if SAE or SADE please fill out SEA or SADE form):

Any complications in relation to airway management?		
Yes	No	If yes: please specify:

Any general complications?		
Yes	No	If yes: please specify:

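### Section 18.7 models the primary outcome as a risk, although it is a count of at least two in every adherent control case, and scopes per subject need not be recorded

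*Combined protocol and SAP*

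**What the plan says.** - **End-point.** Section 4 defines the primary end-point as "Number of times where fiberoptic confirmation of tube position during intubation or surgery is needed". Section 18.3.3 analyses it as a number per procedure, and section 18.5 adds: "Must be stated in integers".
- **Model.** Section 18.7 describes a "decision tree running over a short time period of one year within the hospital setting". Its first effect measure is "The primary outcome: the risk of needing a bronchoscope to check DLT placement", and its second is the cross-infection risk that follows from bronchoscopy. On the cost side, "the average cost per procedure will create the cost input into a cost-effectiveness model".
- **Control procedure.** Section 7.5.2 (steps 11 to 15) has the FOB passed at intubation as a fixed step. Section 7.6 has the position reconfirmed by FOB after the subject is turned to the lateral position.
- **Test procedure.** In sections 7.5.1 and 7.6 the aView image is the routine check, and the FOB is used only if needed.
- **Bronchoscope resources.** Section 7.10 collects these by "following at least 5 bronchoscopes from storage/drying cabinets through procedure, cleaning, reprocessing and back to storage/drying cabinets". It also mentions a worksheet for resources and personnel time, without saying whether it is kept per subject.
- **CRF (Appendix V).** There is a field for the number of bronchoscope uses at intubation and another for surgery, plus one FOB brand and model row. The instruction above that row is "Product information should only be filled out for the products being used". There is no field for the number of scopes.

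**The concern.** A probability of any use and a mean number of uses agree only when no subject has more than one use. The control procedure rules that out, because it requires two. Entered as a risk, the adherent control value is 1 whatever happens later in the case, so the effect term cannot register a third or fourth control-arm use.

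Neither quantity need equal the number of bronchoscopes taken from storage and reprocessed, which is the unit over which section 7.10 gathers resources. Two uses may be one scope used twice or two scopes. Following five or more scopes shows what a cycle consumes. It does not show how many cycles each subject generates in each arm.

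The stated aim (section 2) is the health economic comparison, and the hypothesis (section 3) attributes cost-effectiveness to less FOB use. The affected input is therefore the mechanism under test.

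**Working it through.** **The plan's own figures.** The plan states no saving, unit cost or tube price. Its only numbers for this outcome are the section 18.1 inputs: means 0.37234 (conventional) and 0.01087 (VivaSight-DL), variances 0.23622 and 0.01087.

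- n per arm = (0.23622 + 0.01087) × (1.96 + 1.28)² / (0.37234 − 0.01087)² = 19.852. Twice this is 39.70, rounded to 40, and 40 / (1 − 0.20) = 50. The plan's figures reproduce.
- The inputs behave like yes/no data. 35/94 = 0.37234, with sample variance 0.37234 × 0.62766 × 94/93 = 0.23622. 1/92 = 0.01087, with sample variance 0.01087 × 0.98913 × 92/91 = 0.01087. Section 18.1 is thus numerically consistent with a proportion, although the end-point is a count.

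**Difference per procedure under the written control procedure.** Let u be the FOB uses in a control case, with control risk 1. Let v be the test-arm value, with at most one use per test subject, so that v serves as both risk and mean count.

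- By risk: 1 − v = 1 − 0.01087 = 0.989
- By count, u = 2: 2 − 0.01087 = 1.989
- Ratio: 1.989 / 0.989 = 2.01

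**How far the ratio depends on the assumptions.**

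| Control uses | Test-arm value | By risk | By count | Ratio |
|---|---|---|---|---|
| 2 | 0 | 1.000 | 2.000 | 2.0 |
| 2 | 0.10 | 0.900 | 1.900 | 2.1 |
| 2 | 0.50 | 0.500 | 1.500 | 3.0 |
| 3 | 0.01087 | 0.989 | 2.989 | 3.0 |

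If both section 18.1 means are taken as yes/no data, risk and count coincide (difference 0.36147) and the ratio is 1.0. That reading conflicts with the two control checks in sections 7.5.2 and 7.6.

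**Direction.** Let c be the cost of one scope cycle, and suppose bronchoscopy cost is cycles × c.

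- A fresh scope for each check: the gross saving is 1.989c, and the risk figure (0.989c) understates it about two-fold.
- One scope for both checks: the gross saving is 0.989c, and the count figure (1.989c) overstates it about two-fold.

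**Net saving.** This needs prices that the plan does not give. As an assumption, let the VivaSight-DL tube cost d × c more than the conventional tube.

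- d = 0.25: 1.739 / 0.739 = 2.4
- d = 0.5: 1.489 / 0.489 = 3.0
- d = 0.75: 1.239 / 0.239 = 5.2
- d = 1.0: the risk-based net saving is −0.011c, and the count-based one is +0.989c

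The net ratio is therefore not bounded by two, and even the sign can depend on the input chosen.

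**The case against.** Several points on the other side are fair.

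- **The risk is listed as an effect, not as a cost multiplier.** Section 18.7 takes average cost per procedure as its cost input and nowhere says that cost is risk × cycle cost. This stands. A reader might infer from section 7.10 that bronchoscopy is costed per cycle, but the plan states only that resources are observed over a cycle. What remains is that no rule links recorded uses, cycles and the average cost.
- **A probability is a normal decision-tree input.** It fits the word incidence in section 3 and can be derived from the recorded counts. This also stands, so no data are lost by it. But section 18.7 presents it as the primary outcome, which it is not.
- **The CRF is not the only resource record.** Section 7.10 has a worksheet and allows further costs to be added when found. A reader might infer that scopes per subject could never be recovered. The documents do not support that, because the worksheet's content is left open. The supportable statement is that the plan does not require it to record scopes per subject by arm.
- **Sensitivity analyses are planned.** Section 18.7 varies the major contributors one at a time, and all stochastic variables together. Scopes per procedure is not named, and the plan specifies no data from which to set its range.

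A reader might also infer that the saving could vanish because a stand-by scope is opened and reprocessed in every test case. Section 7.3 does have FOB brand and model recorded for the test group beforehand. However, its itemised preparation table contains no bronchoscope, section 8.3 says only that scopes are available, and the CRF limits product entries to products used. Nothing says that a scope is opened in every test case.

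**Conclusion.** The mismatch is explicit and worth correcting before data collection. Section 18.7 replaces a count with a risk that the control procedure fixes at 1, and the plan does not secure the number of scopes per subject needed to turn uses into cost.

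The size is 0.99 against 1.99 per procedure, a ratio of about 2. It rests on exactly two uses in each control case, adherence to both checks, and a test-arm value of 0.011. It becomes 3 or more with further control uses, and 1.0 only on the yes/no reading of section 18.1.

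This is not a finding that the trial's saving is wrong by a factor of two. The figure concerns gross bronchoscopy only, and its direction depends on whether one scope serves both checks. The sample size arithmetic is unaffected.

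**What to change.** 1. Add one line to the CRF, or to a worksheet kept per subject, in both arms: number of bronchoscopes opened for this subject and number sent to reprocessing.
2. In section 18.7, use mean scopes reprocessed per procedure, by arm, for the bronchoscopy part of the cost.
3. In section 18.7, use mean FOB uses per procedure, which is the actual primary outcome, as the effect. The probability of any use can be reported as a secondary input if wanted.
4. Name scopes per procedure as a parameter in the one-way sensitivity analysis, with its range taken from the recorded data.

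The cost is one extra field and some rewording in section 18.7. The estimated saving may become less favourable to VivaSight-DL.

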## 2. AIM OF THE INVESTIGATION

The aim of this study is to make a health economic evaluation comparing novice physicians use of VivaSight-DL and a conventional DLT for single-lung ventilation during thoracic surgery. To do so, clinical outcomes that influence the cost of the procedures, including the incidence of fibreoptic bronchoscope (FOB) use, time and need of tube repositioning (see section 4), will be assessed and analysed.

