Physicians with experience in less than 50 DLT placements in patients are included in the investigation. The learning curve is accounted for by giving all physicians a training in performing DLT intubation before participating in the study. During the training, the physicians will perform at least 10 conventional DLT placements and three VivaSight-DL placements in manikin. Investigational product training will be recorded on a separate form and stored in the Sponsor File.

The investigation center is regularly performing single lung ventilations and has a patient flow of minimum 5 per week. The center is willing to allow insight to the departments' general costs in relation to surgeries with single-lung ventilation. The extent of necessary cost data depends on the sites' organisational setup and subsequently the resources spent during single-lung ventilation and reprocessing of bronchoscopes. Data is collected after the entire process related to single-lung ventilation has been thoroughly mapped via monitoring and interviewing key personnel. Cost data related to single-lung ventilation includes but is not excluded to personnel costs, capital costs related to bronchoscopy, reprocessing and performing single-lung ventilation, maintenance costs, cost of service agreements, cleaning verification costs and administrative costs.

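### Bronchoscope use is both a cost and an effect in the section 18.7 model, and with no threshold or net-cost condition a device that costs more could be reported as cost-effective

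*Combined protocol and SAP*

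**What the plan says.** **Cost side.** Section 18.7 states: "The cost of all relevant processes related to single-lung ventilation will be summed and the average cost per procedure will create the cost input". Section 5.1 names among the items to be collected "capital costs related to bronchoscopy, reprocessing and performing single-lung ventilation", and section 7.10 adds that "all resources and times related to bronchoscopes will be collected via following at least 5 bronchoscopes from storage/drying cabinets" and back again through cleaning and reprocessing. Each bronchoscopy avoided therefore already lowers the cost of the VivaSight-DL arm.

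**Effect side.** Section 18.7 lists two effects for the same model. The first is "The primary outcome: the risk of needing a bronchoscope to check DLT placement". The second is "The subsequent risk of cross-infection due to bronchoscopy", to be calculated from the literature.

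**Output.** Of the decision tree, section 18.7 says: "This will result in the deterministic ICER". One-way sensitivity analyses, a probabilistic analysis and a cost-effectiveness plane follow. No willingness-to-pay threshold is given, and the plan does not say which of the two effects is the denominator.

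**Aim and hypothesis.** Section 2 places bronchoscope use among "clinical outcomes that influence the cost of the procedures, including the incidence of fibreoptic bronchoscope (FOB) use", that is, as a driver of cost. The alternative hypothesis in section 3 holds that VivaSight-DL is more cost-effective because bronchoscope use is significantly lower. It sets no condition on what the device costs overall.

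**The concern.** A bronchoscopy is a resource. Once its capital, reprocessing and staff costs are in the numerator, and the infection risk it carries is listed as its own effect, the plan names no further value for avoiding one. Yet the avoided bronchoscopy is itself an effect of the ICER. Whoever reads a cost per avoided bronchoscopy must decide what one is worth, and the natural guide is what a bronchoscopy costs. That saving has already been subtracted.

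The health economic evaluation is the stated aim of the study, and section 18.2 has all data analysed by the sponsor. If the rule for judging the ratio is left open, a device with a positive net cost could be called cost-effective, either through a generous value per avoided use or simply because section 3 is read literally.

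**Working it through.** **The plan's own figure.** The documents give no cost, ICER or threshold. The only computed figure tied to this outcome is the sample size in section 18.1:

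(0.23622 + 0.01087) × (1.96 + 1.28)² / (0.37234 − 0.01087)² = 0.24709 × 10.4976 / 0.13066 = 19.852 per arm

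Doubled, this is 39.70, rounded up to 40; 40 / 0.8 = 50. It reproduces, and this point does not affect it.

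**Notation** (none of P, F or L is in the documents)
- P: extra cost of VivaSight-DL per procedure, bronchoscopy excluded
- F: cost of one bronchoscope use
- u: control minus test difference in mean number of uses, which drives cost
- r: control minus test difference in the risk of needing a bronchoscope, which is the effect in section 18.7
- L: value placed on one avoided need

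**Step 1: the ratio.** Incremental cost is P − uF, so ICER = (P − uF) / r. The saving uF appears once. If P > uF and r > 0, both the incremental cost and the ICER are positive.

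**Step 2: the decision.** Judged on cost alone, the device passes when P < uF. Judged against a value L, it passes when (P − uF) / r < L, that is, when P < uF + rL. The limit rises by rL, a factor of 1 + rL/(uF). With L = F the factor is 1 + r/u, which is 2 only when r = u.

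**Step 3: range in units of F.** L is assumed to lie between 0 and F. Three assumed settings are shown:
- The planning difference in section 18.1, 0.37234 − 0.01087 = 0.36147, with r = u assumed.
- One use in every control patient: u = r = 1 − 0.01087 = 0.98913.
- Two uses in every control patient: u = 2 − 0.01087 = 1.98913 and r = 1 − 0.01087 = 0.98913.

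The last two reflect the bronchoscope steps written for controls at intubation (section 7.5.2) and after lateral positioning (section 7.6). In both, 0.01087 is taken as the test arm's mean uses and as its risk.

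| Setting | u | r | Limit, L = 0 | Limit, L = 0.5F | Limit, L = F | Factor at L = F |
|---|---|---|---|---|---|---|
| Planning difference | 0.361 | 0.361 | 0.361F | 0.542F | 0.723F | 2.0 |
| One control use | 0.989 | 0.989 | 0.989F | 1.484F | 1.978F | 2.0 |
| Two control uses | 1.989 | 0.989 | 1.989F | 2.484F | 2.978F | 1.5 |

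The first row is only indicative: section 18.1 describes scopes used to correct placement, whereas the effect in section 18.7 is needing one to check it.

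**Step 4: one case.** In the first setting take P = 0.542F. Incremental cost is 0.542F − 0.361F = +0.181F and the ICER is 0.181F / 0.361 = 0.5F per avoided use. Net benefit is rL − (P − uF): −0.181F at L = 0, and 0.361F − 0.181F = +0.181F (unrounded 0.1807F) at L = F. The data are the same and the conclusion is opposite.

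**Step 5: section 3 read literally.** A significantly lower bronchoscope incidence supports the claim of cost-effectiveness whatever P is. That is looser than any limit in the table.

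**The case against.** A reader might infer that the ratio itself counts the saving twice. It does not: Step 1 subtracts uF once, and the denominator is in natural units, not money. Netting event costs above and events avoided below is the ordinary form of a cost per event avoided. A net-cost device also stays visible, because section 18.7 calls for a table of costs, risks and base case and for a cost-effectiveness plane. All of this stands.

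A reader might also infer that the break-even premium doubles. That needs a value per avoided need equal to F, which the plan never states, and a risk difference equal to the difference in uses. If every control patient has two uses, the factor at L = F is about 1.5. A threshold of zero, or one that leaves out the bronchoscope's resource cost, adds no second credit. This also stands.

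Finally, section 3 can be read as giving the mechanism, with section 18.7 doing the economic work. That is a fair reading, but section 18.7 supplies no rule for concluding that the device is or is not cost-effective. Section 3 is then the only place where such a conclusion is tied to a result, and there it is tied to bronchoscope incidence.

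**Conclusion.** The point holds as a gap in the decision rule, not as an arithmetic error. Bronchoscope use feeds both cost and effect, its named health consequence is listed separately, no threshold is given, and section 3 does not require a favourable net cost. A device with a positive net cost could therefore be reported as cost-effective, and any value per avoided bronchoscopy that reflects its own cost would credit the saving again when the ratio is judged.

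The size is rL per procedure and cannot be computed from the documents. For L between 0 and F, the assumed settings give a break-even premium between 1 and 2 times the cost-neutral one. If VivaSight-DL turns out to be cost-saving (P < uF) and bronchoscope use falls, the question does not arise. The primary test and the sample size are unaffected.

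**What to change.** 1. In section 18.7, make the mean incremental cost per procedure, bronchoscope costs included, the main economic result. Give its 95% interval from the probabilistic analysis, and base any claim of economic advantage on it.
2. Beside it, report bronchoscope use, repositionings, surgical restriction and airway complications as consequences. All are already on the case report form.
3. If a cost per avoided bronchoscopy is kept, label it secondary, and do not judge it against a value that includes the resource cost of the bronchoscopy.
4. Amend the alternative hypothesis in section 3, and the null to match, so that cost-effectiveness is not concluded from bronchoscope incidence alone.

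The cost is wording in two sections, settled before the data are analysed. Data collection and the decision tree stay as they are. The downside for the sponsor is that the result may look less favourable than a cost per bronchoscopy avoided.
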